3.0 TRIAL DESIGN

This is an open-label, randomized, multicenter, Phase 2 trial in 100 adult male and female patients with treatment-naïve, Stage IV/metastatic NSCLC whose tumors are not known to have EGFR mutations or ALK rearrangements, but have high expression ($\geq 50\%$) PD-L1 as determined with an FDA-approved PD-L1 IHC 22C3 assay.

Patients will be stratified according to tumor histology (squamous vs non-squamous).

Patients will be randomized in a 1:1 ratio into 1 of 2 treatment arms (Figure 1).

[figure not shown]

Figure 1. Trial Design

Trial sites will provide best supportive care per institution's standard of care including concomitant medications.

Arm 1 and 2 treatment will continue in the absence of disease progression, unacceptable toxicity, or patient's withdrawal of consent. Patients will be treated with a maximum of 35 cycles of pembrolizumab every 3 weeks or 2 years, whichever is longer.

All radiological assessments will include at minimum, scans of the head, chest, abdomen, and pelvis.

At the time of documented disease progression (by Investigator assessment) patients in Arm 1 will be discontinued from the treatment period of the trial and continue on the follow-up period. At the time of documented disease progression (by Investigator assessment), patients in Arm 2 may crossover to receive treatment with AM0010 and pembrolizumab.

Confirmation of complete response (CR) or partial response (PR) is required. Confirmatory scans will be performed as follows:

- CR and PR criteria per RECIST v1.1 must be met again at least 4 weeks after initial documentation.

Patients with suspected pseudoprogression on scans in the absence of clinical deterioration should remain on trial treatments and be rescanned at 4 weeks or later as outlined in Section 7.6.

If progression is confirmed on follow up scan, then discontinue treatments and follow trial procedures for end of treatment and survival follow-up or procedures for crossover patients.

Scans will include head and CAPs and will be sent to the central imaging vendor for archiving and possible assessment at a later date. If clinical progression is suspected, all relevant clinical documentation is to be submitted to the central imaging vendor.

For patients who were randomized, but withdraw consent, survival (date of death) will be obtained by use of publicly available information.

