3.2 Number of Patients

Approximately 100 (50 within each treatment arm)

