5.1 Treatment Arms

Patients will be randomized in a 1:1 ratio into one of two arms according to histology type (squamous vs non-squamous) as follows:

- Arm 1: Patients will receive AM0010 and pembrolizumab
- Arm 2: Patients will receive pembrolizumab alone

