7.8 Continued Treatment

7.8.1 Crossover

At the time of disease progression (as assessed by the Investigator) patients randomized to trial Arm 2 may crossover to study Arm 1 to receive AM0010 and pembrolizumab. When progressive disease is noted on the scan for an Arm 2 patient, no more than 21 days should pass before the patient crosses over to Arm 1. The scans and/or clinical assessment at crossover will be used as a new baseline to determine response or PD on Arm 1.

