SAEs which are considered related to study drug occurring >90 days after last trial treatment must be reported on both a CRF and on a SAE Report Form (with an autopsy report if available).

Investigators are not obligated to actively seek AEs or SAEs in patients once they have discontinued (the patient summary CRF has been completed). However, if the investigator learns of any SAE, including a death, at any time after a patient has been discontinued from the study, and he/she considers the event reasonably possibly related to the study treatment or study participation, the investigator must promptly notify Lilly or its designee.

Lilly will periodically review evolving aggregate safety data within the study by appropriate methods.

If it is deemed to be in the best interest of the patient to start a new anti-cancer treatment prior to the follow-up visit, the visit duration may be shortened. In this case, the follow-up assessments should be completed prior to the initiation of the new therapy. If an anti-tumor treatment is initiated within 90 days of the last dose of trial treatment, the start date of this treatment should be documented on the appropriate CRF.

The Investigator must notify the IRB of SAEs occurring at the site and other AE reports received from Lilly/designee in accordance with local procedures/site IRB policies.

It will be left to the Investigator’s clinical judgment whether or not an AE is of sufficient severity to require the patient’s removal from treatment. A patient may also voluntarily withdraw from treatment due to what he or she perceives as an intolerable AE. If either of these occurs, the patient must undergo an end-of-treatment assessment and be given appropriate care under medical supervision until symptoms cease or the condition becomes stable. If the patient is permanently withdrawn from the trial or investigational product due to an SAE, this information must be included in either the initial or follow-up SAE Report Form or the End-of-Treatment CRF.

Study site personnel must report any treatment discontinuations that result from AEs to Lilly or its designee via eCRF, clarifying, if possible, the circumstances leading to the discontinuation of treatment.

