13.3 Trial Monitoring and Data Collection

The Lilly representative and Regulatory Authority inspectors are responsible for contacting and visiting the Investigator for the purpose of inspecting the facilities and, upon request, inspecting the various records of the clinical trial (eg, CRFs and other pertinent data) provided that patient confidentiality is respected.

The Lilly monitor/designee is responsible for verifying the CRFs at regular intervals, approximately once per month, throughout the trial to verify adherence to the protocol, completeness, accuracy, and consistency of the data; and adherence to local regulations on the conduct of clinical research. The monitor should have access to patient medical records and other trial-related records needed to verify the entries on the CRFs.

The Investigator agrees to cooperate with the monitor to ensure that any problems detected in the course of these monitoring visits, including delays in completing CRFs, are resolved.

In accordance with ICH GCP and the Sponsor's audit plans, this trial may be selected for audit by representatives from Lilly Clinical Quality Assurance Department (or designees). An inspection of site facilities (eg, pharmacy, drug storage areas, and laboratories) and a review of trial-related records will occur to evaluate the trial conduct and compliance with the protocol, ICH GCP, and applicable regulatory requirements.

If an anti-tumor treatment is initiated within 90 days of the last dose (AM0010/pembrolizumab), the start date of this treatment should be documented on the appropriate CRF, and no further recording of concomitant medications will occur unless it is to treat AM0010-related AEs.

To ensure the quality of clinical data across all patients and sites, a clinical data management review will be performed on patient data received at Lilly or its designee. During this review, patient data will be checked for consistency, omissions, and any apparent discrepancies. In addition, the data will be reviewed for adherence to the protocol and GCP. To resolve any questions arising from the clinical data management review process, data queries and/or site notifications will be sent to the site for completion and returned to Lilly or its designee.

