## 6. A Priori Statistical Methods

### 6.1. General Considerations

#### 6.1.1. Population

**Enrolled Population:** all patients who signed the informed consent form and were registered into the interactive web response system (IWRS).

**Intent-to-Treat (ITT) population:** all randomized patients per the IWRS.

Unless otherwise noted, all disposition analyses will be performed on the ITT population, all patient characteristic and efficacy analyses will be performed on the ITT population and all safety and exposure analyses will be performed on the Safety population.

All analyses will be performed by treatment arm. Unless otherwise noted, all analyses on the ITT population will be performed by assigned treatment arm and all analyses on the safety population will be performed by actual treatment received.

**Per-Protocol Population:** all patients who are in the safety population and have no important protocol deviations.

The important protocol deviations which will result in exclusion from the Per-Protocol population are listed below. This is not an exhausted list and may be amended over the course of the trial. The final list will be provided as an appendix to this SAP before performing the primary analysis of this study (i.e. approximately 6 months after last patient randomized).

- patients with disease histology other than NSCLC
- patients with European Cooperative Oncology Group (ECOG) >1 at baseline
- patients who received prior regimen in metastatic setting
- patients who do not have measurable disease at baseline
- patients receiving the incorrect randomized treatment assignment (any amount of duration)

**Response Evaluable Population:** all patients who are randomized and received any amount of study medication, have baseline adequate tumor assessment, and at least 1 post-baseline adequate tumor assessment.

**Safety Population:** all randomized patients who received any amount of study medication, AM0010 or pembrolizumab.

**PK Population:** all patients who are treated with available serum time-concentration data from randomized patients.

**Biomarker Population:** includes all patients who are treated with available biomarker data from randomized patients.

**ADA Evaluable population:** all patients who are treated (in safety population), have baseline ADA (anti-drug antibody) result, and at least one post-baseline ADA result.

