#### **6.4.6. Concomitant Medications**

All medications will be coded to the generic preferred name according to the current World Health Organization (WHO) drug dictionary. All concomitant medications will be summarized for the ITT population using the preferred name.

Selected concomitant medication such as steroid use will be summarized separately.

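### After new anti-tumor therapy starts, only medication for AM0010-related AEs is still recorded, so late concomitant-medication recording differs by arm; the net effect is probably small and can go either way

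*Protocol*

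**What the plan says.** Protocol 13.3 covers patients who begin another anti-tumor treatment within 90 days of their last dose of AM0010 or pembrolizumab. The start date goes on the CRF, and from then on "no further recording of concomitant medications will occur unless it is to treat AM0010-related AEs". The trigger covers both study drugs; the exception names only one.

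On exposure, Protocol 5.1 states: "Arm 2: Patients will receive pembrolizumab alone". At progression the arms part ways. Under Section 7.8.1, "patients randomized to trial Arm 2 may crossover to study Arm 1 to receive AM0010 and pembrolizumab", while under Section 3.0 "patients in Arm 1 will be discontinued from the treatment period of the trial and continue on the follow-up period".

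On use of the data, SAP 6.4.6 summarizes all concomitant medications on the ITT population and adds: "Selected concomitant medication such as steroid use will be summarized separately". SAP 6.1.1 states: "All analyses will be performed by treatment arm", with ITT analyses following the assigned arm. No test is planned on these data.

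Protocol 9.3 keeps AE recording open whatever the attribution. It also repeats the instruction to document the start of new therapy, without the medication cut-off. No other section restores the entries that 13.3 drops.

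**The concern.** A by-arm table is interpretable only if the same recording rule ran in both arms. Here a late steroid course for an AE attributed to AM0010, or to both drugs, stays on record, while one for an AE attributed to pembrolizumab alone does not. An Arm 2 patient who never crosses over can only be in the second group. The trial is open-label and attribution is the investigator's judgement, so in Arm 1 the record also depends on that judgement.

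At stake is the descriptive comparison of concomitant medication, steroids above all. Safety and tolerability is a secondary objective on which the arms are compared (SAP 4.2), so the medication used to manage toxicity should be captured even-handedly.

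**Working it through.** **Step 1. Who can still generate a record after new therapy starts**

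| Patient | AE being treated is attributed to | Recorded under 13.3? |
|---|---|---|
| Arm 1 | AM0010, alone or with pembrolizumab | Yes |
| Arm 1 | pembrolizumab only | No |
| Arm 2, never crossed over | pembrolizumab | No |
| Arm 2, crossed over | AM0010, alone or with pembrolizumab | Yes |
| Any | neither drug | No |

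Strictly, the rule differs by AM0010 exposure. It differs by arm because every treated Arm 1 patient is meant to receive AM0010 and only crossover patients do in Arm 2.

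**Step 2. Inputs**

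The plan gives no figure on this point to reproduce. The only documented input is 50 patients per arm (Protocol 3.2), so one patient is 1/50 = 2 percentage points. The rest are assumptions:

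- n1, n2: never-crossed-over patients in Arm 1 and Arm 2 who start new therapy within 90 days.
- p: share of them whose only steroid course is for a treatment-related AE, begins after that start, and falls within the existing collection period; taken as equal in both arms.
- a: share of those Arm 1 courses attributed to AM0010 or to both drugs.

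**Step 3. Formula, setting crossover patients aside**

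The recorded share falls by p × n1 × (1 - a)/50 in Arm 1 and by p × n2/50 in Arm 2. The shift in the Arm 1 minus Arm 2 difference is therefore

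p × (n2 - n1 × (1 - a))/50 = p × (n2 - n1)/50 + p × n1 × a/50.

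The first term arises because recording stops for unequal numbers of patients. The second is the AM0010 exception itself and can only add to Arm 1. The total is zero when n2 = n1 × (1 - a).

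**Step 4. Results, in percentage points, p = 5%**

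| n1 | n2 | a | Unequal counts | Exception | Total |
|---|---|---|---|---|---|
| 20 | 20 | 0.5 | 0 | +1.0 | +1.0 |
| 20 | 10 | 0.5 | -1.0 | +1.0 | 0 |
| 30 | 10 | 0.5 | -2.0 | +1.5 | -0.5 |
| 30 | 5 | 0 | -2.5 | 0 | -2.5 |
| 30 | 30 | 1 | 0 | +3.0 | +3.0 |

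The last two rows are the extremes over n1 and n2 from 5 to 30 and a from 0 to 1. Results scale with p: at 1% the extremes are -0.5 and +0.6, and at p = 0 the shift is zero.

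**Step 5. Sensitivity to p**

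Take n1 from 10 to 25, n2 from 5 to 25 and a from 0 to 0.6. At p = 10% the extremes are 0.10 × (5 - 25)/50 = -4.0 and 0.10 × (25 - 10 × 0.4)/50 = +4.2 points. At p = 20% they double to -8.0 and +8.4. Calling the effect small therefore rests on p being small.

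**The case against.** The strongest objection is that little may be left to lose. Protocol 7.9 lists concomitant medications at the end-of-treatment visit, 28 days (±7) after the last dose; Section 7.10 does not list them among the later follow-up items, and Appendix A shows no mark for them at days 60 and 90. When new therapy is to start early, Section 9.3 says "the follow-up assessments should be completed prior to the initiation of the new therapy". If collection ends at that visit, the exception hardly operates. This limits the size but does not remove the asymmetry: a 90-day trigger with an exception makes sense only if recording can continue after new therapy begins.

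Second, every rate above is assumed, and the extremes are unlikely corners. The -2.5 needs a = 0, where the exception retains nothing and only unequal counts act. The +3.0 needs 30 of 50 Arm 2 patients to start other therapy without crossing over. For steroids a low a is plausible, since Protocol 1.3 says AM0010 alone did not cause autoimmune toxicity and the corticosteroid guidance in Table 4 is for pembrolizumab's immune-related AEs. That stands. It also means the exception suits the steroid summary poorly: late courses attributed to pembrolizumab alone are lost in both arms.

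Third, SAP 6.4.6 states no time window, so it is not certain that late entries reach the table; it does, however, refer to all concomitant medications.

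Fourth, giving priority to data on the only unapproved drug is defensible. That may explain the wording, but it does not suit a table that compares arms.

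**Conclusion.** The concern holds as a minor point. Section 13.3 sets a recording rule that depends on AM0010 exposure and hence on arm, and SAP 6.4.6 and 6.1.1 carry those records into by-arm summaries. Under the assumptions of p at most 5% and 5 to 30 never-crossed-over patients per arm starting new therapy within 90 days, the distortion of the steroid difference lies between -2.5 and +3.0 points. It may be zero. The direction is not fixed because only Arm 2 has a crossover option at progression, so the numbers starting other therapy can differ by arm. That the net effect is small is a judgement: the documents supply none of the rates.

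The finding is limited to medication records first made after new therapy starts. Earlier entries stay on record, AEs and SAEs are captured whatever their attribution, and subsequent therapy is collected for all randomized patients. No efficacy endpoint uses these medication records.

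**What to change.** In Protocol 13.3, replace *AM0010-related AEs* with *AEs related to study treatment (AM0010 and/or pembrolizumab)*, applied identically in both arms over the existing concomitant-medication collection period. SAP 6.6.2 already counts an AE in the combination arm as related if it is attributed to either drug or both, so the wording is consistent with the plan. The courses counted in p would then be kept in both arms, and both terms of the shift would disappear. Medication for unrelated conditions would still stop being recorded, under the same rule for everyone.

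The cost is a one-phrase amendment and a few more entries on an existing CRF page, with no new visit and no longer collection period. If collection has mostly closed before new therapy starts, few entries are added.

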13.4 Language

All written information and other material to be used by patients and investigative staff must use vocabulary and language that are clearly understood.

13.5 Publication Policy

To coordinate the dissemination of data from this trial, a publication committee may be formed consisting of both Principal Investigators and appropriate Lilly staff. The committee is expected to solicit input and assistance from other Investigators and Lilly staff as appropriate. Membership on the committee (both for Investigators and Lilly staff) does not guarantee authorship. The criteria described below should be met for every publication.

Authorship of any publications resulting from this trial will be determined on the basis of the Uniform Requirement for Manuscripts Submitted to Biomedical Journals (International Committee of Medical Journal Editors, 2016), which states:

- Authorship credit should be based on (1) substantial contributions to conception and design, acquisition of data, or analysis and interpretation of data; (2) drafting the article or revising it critically for important intellectual content; (3) final approval of the version to be published. Authors should meet conditions 1, 2, and 3.
- When a large, multi-center group has conducted the work, the group should identify the individuals who accept direct responsibility for the manuscript. These individuals should fully meet the criteria for authorship defined above.
- Acquisition of funding, collection of data, or general supervision of the research group, alone, does not justify authorship.
- All persons designated as authors should qualify for authorship, and all those who qualify should be listed.
- Each author should have participated sufficiently in the work to take public responsibility for appropriate portions of the content.

All publications (eg, manuscripts, abstracts, oral/slide presentations, book chapters) based on this trial must be submitted to Lilly for corporate review. The Clinical Trial Agreement between the institution, principal Investigator, and Lilly will detail the procedures for and timing of Lilly review of publications.

15.0 APPENDICES

Appendix A – Schedule of Assessments

Assessments Both trial Arm 1 and Arm 2 will follow the same schedule of assessments unless otherwise noted.	Screening	Clinic Visit (Cycle)			End of Treatment	Extended Safety Observation Period	Long-Term Follow-Up
	Within 21 Days of Randomization	1, 3, 5, etc. ±3 Days	2 ±3 Days	4, 6, 8, etc. ±3 Days	28 Days ±7 Days from Last Dose	60 and 90 Days ±7 Days from Last Dose	
GENERAL and SAFETY AWARENESS							
Informed Consent	X						
Medical/Cancer History and Demographics	X						
Physical examination (include Ht [screening only] and Wt)	X	X			X		
Vital signs	X	X			X		
ECOG performance status	X	X			X		
12-Lead ECG	X	X			X		
Concomitant Medication	●				●		
Adverse Event	Post Randomization	●			●		
Survival ^a and Treatment Status							X
LABORATORY ASSESSMENTS							
Hematology, Chemistry	X	X	X	X	X		
aPTT and INR or PT	X	X	X	X	X		
Thyroid Function Test (TSH, T3, and T4)	X	X			X		
Pregnancy Test	X	X			X		
Urinalysis	X	X			X		
PD-L1 Status	X ^b						
Submission of tumor sample for biomarker research		X ^c					
TRIAL TREATMENT ARM 1 and ARM 2							
Arm 1 AM0010		Self-Administration QD SQ					
Arm 1 and Arm 2 Pembrolizumab		200 mg 30 min IV Q3W					
IMAGING ASSESSMENT							
Tumor Assessment ^d	Within 30 days of randomization	X				X	X
ADA, PK and Biomarker BLOOD SAMPLES							
ADA (required Arms 1 and 2) ^e		X	X	X	X	X	
PK (required Arm 1 and crossover) ^e		X	X	X	X	X	
Biomarkers (required Arms 1 and 2) ^f		X	X		X		

^a All randomized patients will be followed for OS every 9 weeks (±7 days) during the first year from the 90-day follow-up visit, every 12 weeks (±7 days) during the second year, and every 16 weeks (±7 days) thereafter. The survival follow-up will be conducted until death or the study completion, whichever is first, whether or not trial drug was administered.

^b A fresh tissue biopsy is only required if no archival tissue is available within 60 days of informed consent or unless approved by the Medical Monitor.

^c Mandatory tumor tissue sample for biomarker research should be submitted once the patient is enrolled (preferably from the same block used for PD-L1 testing).

^d Tumor assessment will be performed for all randomized patients every 9 weeks (±7 days) during the study treatment and during the first year from discontinuation of the study treatment, every 12 weeks (±7 days) during the second year, and every 16 weeks (±7 days) thereafter. Tumor assessment will be repeated until disease progression, death, or receipt of new anti-cancer therapy, or until study completion, whichever is first, whether or not study treatment was administered. A baseline tumor assessment is required at crossover.

^e ADA and PK samples will be collected on Day 1 of Cycles 1, 2, 3, 4, every fourth cycle thereafter, and at end of treatment visit, and at the follow-up visits 60 and 90 days after the last dose of study treatment.

^f Specific biomarker blood collection tubes may vary by time point. See the Lab Manual for details.

Appendix B – Continued-Access Period Assessments

	Continued-Access Treatment Visits ± 3 Days	Continued-Access Follow-Up Visits 28, 60, and 90 days ± 7 Days after the Last Dose of Study Treatment
Arm 1 AM0010	X	
Arm 1 and Arm 2 Pembrolizumab	X	
Adverse event	X	X
ADA ^a	X	X
PK ^a	X	X

^a ADA and PK samples will be collected on Day 1 of every 4th cycle during the continued access treatment visits and at the continued access follow-up visits 28-, 60-, and 90-days after the last dose of study treatment.

